## Study Objectives

To increase rates of MH care initiation, we propose an automated TM intervention, “Text to Connect” (T2C), that aims to increase motivations in at-risk adolescents and their parents. We will develop and examine T2C using dissemination and implementation science principles, specifically, the RE-AIM framework, for balancing internal and external validity and optimizing uptake and sustainability. We will select the most salient of the following behavior change techniques: psychoeducation, cued mood monitoring, adolescent-parent communication prompts, cognitive bias modification, and cues to action. Intervention material will be tailored to baseline characteristics. We will begin with treatment development. In an initial usability phase, we will develop and iteratively refine the format and content of T2C based on feedback from stakeholders. Data will inform a subsequent feasibility trial comparing T2C with treatment as usual (TAU) using a stepped wedge design.

Aim 1 (Phase 1, Development). To develop T2C, a TM intervention to address motivational barriers to MH treatment initiation for depression and/or suicidal screen-positive adolescents and parents in pediatric primary care. We will collaborate with NuRelm and the Office of Academic Computing at WPIC and the Methods Core to develop T2C based on stakeholder feedback (adolescents, parents, pediatricians, MH clinicians).

Aim 1b (Phase 1b, Feasibility). To examine the feasibility of T2C in pediatric primary care clinics (n=2 clinics, 50 adolescents) using a stepped wedge design.

Hypothesis 1b: Readiness for MH care will be greater among adolescents in T2C vs adolescents referred during TAU. We will first conduct t tests for continuous variables and chi square tests for categorical variables to examine for baseline differences in demographic

and clinical variables. We will use generalized linear mixed models (nesting for site) to examine for between-intervention differences in readiness. Baseline characteristics that distinguish the groups will be included as covariates in models examining treatment effects.

Aim 2: Explore differential rates of service utilization (behavioral and physical health services) among youth who receive Text2Connect (T2C) versus Treatment As Usual (TAU).

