#### Baseline assessment phone call:

Following the informed consent, the ARC assessor will conduct the baseline assessment measures. The measures include collecting sociodemographic questions, the CSSRS scale & suicide scales, quality of life ratings, treatment history, barriers to treatment, readiness for treatment, attitudes toward seeking psychological help, anxiety & mania adaptive scales via the K-CAT mental health adaptive screen, substance use, depression history, treatment preferences, and if there's a family history of bipolar disorder that impacts the youth's risk for mental health problems. A waiver of HIPAA authorization to collect permission verbally over the phone will be used to access and collect medical record data. Electronic medical record information will be used to supplement treatment and service utilization and uptake of the T2C intervention via the RE-AIM framework described in statistical analysis. Parents will respond to questions about their child, not themselves and youth will answer about themselves. Phone calls will take about 30-60 minutes.

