## **Statistical Considerations**

A stepped wedge design was selected for both ethical considerations and feasibility. A stepped wedge cluster randomized trial design involves the sequential random rollout of an intervention over multiple time periods following a “baseline” period when no cluster has been exposed. The

crossover is typically in one direction, from control to intervention, and continues until all of the clusters receive the intervention with observations taken from every cluster and at each time period. All 3 studies in the ETUDES Center, and specifically, T2C, will utilize this design. Prior to study start, each CCP study practice will be randomly assigned to switch from Treatment As Usual (TAU) to the intervention.

In the proposed stepped wedge design, all practices start with TAU (i.e., PCP referral to embedded MH care) and are randomized to transition to implement T2C at different times. All clinics will be initially monitored for at least 2 months during TAU, followed by a staggered adoption of T2C. During each time period, a new clinic will begin to use T2C (order determined by block randomization. A web-based system will randomly assign the next clinic to begin.

With regard to Hypothesis 1: We will conduct t tests for continuous variables and chi square tests for categorical variables to examine for baseline differences in demographic and clinical variables. We will use generalized linear mixed models (nesting for site) to examine for between-intervention differences in readiness. Baseline characteristics that distinguish the groups will be included as covariates in models examining treatment effects.

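### Baseline significance tests choose the model covariates, which is a weak guard against case-mix change with 50 youths in two clinics; a short fixed list would be better

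*Combined protocol and SAP*

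**What the plan says.** Study Objectives (Hypothesis 1b) and Statistical Considerations give the same two-step rule. First come "t tests for continuous variables and chi square tests for categorical variables to examine for baseline differences in demographic and clinical variables". Then: "Baseline characteristics that distinguish the groups will be included as covariates in models examining treatment effects".

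The outcome model is described separately: "We will use generalized linear mixed models (nesting for site) to examine for between-intervention differences in readiness". Site is mentioned there only, and the baseline tests carry no clinic term. No significance level defines what counts as distinguishing the groups, and no covariate is named in advance.

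The setting is "pediatric primary care clinics (n=2 clinics, 50 adolescents) using a stepped wedge design". What is randomised is the order in which clinics switch, and on timing the plan says "All clinics will be initially monitored for at least 2 months during TAU, followed by a staggered adoption of T2C". The TAU:T2C split of the 50 youths and each clinic's share of T2C youths are not given.

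The baseline call already collects plausible prognostic variables, among them "sociodemographic questions, the CSSRS scale & suicide scales, quality of life ratings, treatment history".

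**The concern.** TAU and T2C youths are enrolled at different calendar times and are not allocated individually. Referral also depends partly on provider judgement (Eligibility Criteria). The kind of youth enrolled could therefore differ between phases, and the test-then-adjust rule is the only covariate safeguard the plan states.

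It has three weaknesses.

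- At this sample size the tests miss most small and moderate shifts.
- They select on observed imbalance, not on relation to readiness, so a strong predictor that happens to look balanced is left out and its precision is lost.
- They pool the clinics. If the staggered switch gives the clinics different T2C shares, a difference between clinics can hide a real shift within clinics, or exaggerate it.

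At stake is how the Hypothesis 1b comparison of readiness is read. The main model also stays undefined until the data are seen, because no threshold is stated.

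**Working it through.** The plan states no power, test level or covariate calculation, so there is no figure to reproduce.

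**Inputs.** From the plan: 50 youths, 2 clinics, t and chi-square tests, site in the outcome model. Assumed: 25 v 25; two-sided 0.05; covariate and readiness each with within-group SD 1; covariate-readiness correlation ρ of 0.5, 0.3 or 0.2; and, where clinic enters, two clinics of 25 with T2C shares of 17/25 and 8/25 (about 2/3 v 1/3).

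**1. Chance that a real shift is flagged.** For a shift of d SD the noncentrality is d / √(1/25 + 1/25) = d / 0.283, with 48 degrees of freedom.

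| Shift d (SD) | Noncentrality | Flagged |
|---|---|---|
| 0.3 | 1.06 | 18% |
| 0.4 | 1.41 | 28% |
| 0.5 | 1.77 | 41% |
| 0.8 | 2.83 | 79% |

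The rate passes 50% only at about 0.57 SD. For a binary variable, 50% v 70% is flagged in 30% of trials and 50% v 80% in 61%. With looser tests the 0.5 SD shift is flagged in 54% (level 0.10) or 68% (level 0.20).

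**2. Bias left in the T2C effect.** Without adjustment the bias is ρ × d. For d = 0.4 that is 0.20, 0.12 and 0.08 SD at ρ = 0.5, 0.3 and 0.2. The rule and fixed adjustment were compared by simulation with clinic in the model and no clinic difference.

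| ρ | Bias, rule | Bias, fixed | RMSE, rule | RMSE, fixed |
|---|---|---|---|---|
| 0.5 | 0.10 | 0.00 | 0.30 | 0.27 |
| 0.3 | 0.05 to 0.06 | 0.00 | 0.31 | 0.30 |
| 0.2 | 0.04 | 0.00 | 0.31 | 0.31 |

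About half the bias remains, although 72% of trials go unflagged, because the unflagged trials are those with the smaller observed differences. False positives for the T2C effect stay near 5% here.

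**3. Effect of pooling the clinics.** Under the assumed shares, 17/25 of T2C youths but only 8/25 of TAU youths come from one clinic. A clinic difference of 0.8 SD therefore adds (0.68 − 0.32) × 0.8 = 0.29 SD to, or takes it from, the pooled comparison. A real 0.4 SD shift then appears as about 0.11 or 0.69 SD. With ρ = 0.5:

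| Clinic difference | Flagged | Bias, rule | False positives |
|---|---|---|---|
| 0.8 SD, opposite to the shift | about 5% | 0.18 | about 9% |
| None | 28% | 0.10 | about 5% |
| 0.8 SD, same direction | 61% | 0.03 | about 4% |

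With no real shift, the 0.8 SD clinic difference alone is flagged in 14% of trials. The resulting bias is only −0.03 SD and false positives are 4.4%, because site is already in the model. With near-equal clinic shares the flag rate is not inflated.

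**4. Would better tests be enough?** Adding clinic to the test, at the same shares, flags a 0.3 SD within-clinic shift in 16% of trials and a 0.5 SD shift in 37%. At level 0.20 the masked case still leaves a bias of 0.14 SD and 7% false positives.

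**The case against.** The strongest reply has five parts.

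- **The rule has a merit that a fixed list lacks.** It screens all the measured demographic and clinical variables. If the variable that shifts is not on the list, a 0.4 SD shift at ρ = 0.5 leaves the full 0.20 SD, against about 0.10 under the rule; for 0.8 SD it is 0.40 against 0.04 to 0.05. This stands. A reader might infer that the imbalance check should simply be dropped, and these figures show why it should not.
- **The gain depends on ρ.** The documents give no correlation between readiness and age, suicide scores or prior treatment. At 0.2 to 0.3 the RMSE advantage is slight. This stands.
- **Masking is only one of two signs.** Nothing in the documents makes a clinic difference opposite to the shift more likely than one in the same direction. A reader might also infer that the design itself fixes a 1:2 v 2:1 clinic mix. It does not: it gives staggered switching and a minimum TAU period, with no recruitment by clinic.
- **Picks that reflect clinic alone do little harm.** A reader might infer that they crowd out real confounders, but the rule sets no limit on the number of covariates, so one pick displaces no other. Nor can a chance of any spurious pick be firmly stated: treating 14 baseline domains as independent would give 1 − 0.95^14 = 51%, but several of the scales are related.
- **This is a feasibility trial.** A bias of 0.04 to 0.10 SD is small beside an RMSE of about 0.30. This limits the importance of the point. It does not remove it, because Hypothesis 1b is comparative.

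**Conclusion.** The point holds as a modest improvement. Letting baseline tests define the main model is a weak guard against case-mix change in this design. For a 0.4 SD shift it leaves a bias of about 0.04 to 0.10 SD as ρ runs from 0.2 to 0.5, where fixed adjustment for the same covariate leaves about none. Unequal clinic shares can make this worse or better.

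The figures rest on a 25:25 split, a 0.05 level, the stated clinic shares and the range of ρ, none of which the plan gives.

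A reader might infer that confounding is left in most trials. The documents do not support that: they give no evidence that a shift occurs, shifts above about 0.57 SD are usually caught even at 0.05, and the unstated threshold may be looser (at 0.20 the 0.4 SD shift is flagged in 55% of trials and the bias falls to about 0.035 SD). The change is worth considering and is not a condition for the trial's validity.

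**What to change.** In Study Objectives (Hypothesis 1b) and in Statistical Considerations:

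- Before outcome data are seen, name a short list of prognostic covariates already collected, for example age, baseline suicide-scale score and prior mental health treatment. Enter it in every T2C effect model whatever the observed imbalance.
- Replace the baseline tests by a descriptive table by phase within clinic, with standardised differences.
- Keep adjustment for any other imbalanced variable as a labelled sensitivity analysis, not as the rule that defines the main model.

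The cost is wording in two sections, no new data and about three degrees of freedom out of 50 youths. Little is gained if the chosen covariates are only weakly related to readiness. The main model gives no protection against a shift in a variable not on the list, which is why the sensitivity analysis should stay.

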## Eligibility Criteria

### **Youth Inclusion Criteria:**

- Youth aged 12-26 yo
- Own a cell phone with text message capability
- Biological or adoptive parent is willing to provide informed consent for teen to participate
- Youth speaks and understands English

-Positive PHQ score or provider determines youth has depressive symptoms based on clinical interaction and refers youth to the study (in cases when PHQ is not available and study staff will complete the PHQ during the screening) OR Provider can refer if they are unclear if symptoms are depressive and PHQ scoring will be used to determine youth's eligibility. OR Screening Wizard screening questionnaire (which includes the PHQ and depressive symptom questions) indicates depression OR provider indicates there is a concern that youth has mood or behavioral problem.

-Referred to mental health care OR screening wizard questionnaire (which indicates if provider makes referral to mental health care)

PHQ-9 scores:

Score of 8 or higher on PHQ-8 -or-

Score of 1 or higher on #9 of PHQ-9 suicidality item

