#### **Youth Exclusion Criteria:**

- Non English speaking
- No parent willing to provide informed consent
- No cell phone with text messaging capability
- Is currently experiencing mania or psychosis
- Evidence of an intellectual or developmental disorder (IDD)
- Life threatening medical condition that requires immediate treatment
- Other cognitive or medical condition preventing youth from understanding study and/or participating.
- Not referred to mental health care

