In order to enhance uptake of T2C, we will conduct the proposed work within the RE-AIM framework, as follows. (R)each: The percentage and characteristics of screen-positive adolescents referred for MH treatment who are offered, and agree to participate in, T2C. (E)fficacy: The impact of T2C on MH treatment initiation and engagement. (A)doption: The percentage and characteristics of PCPs who refer to T2C upon making a referral for MH care for a screen-positive adolescent. (I)mplementation: The percentage and characteristics of patients who consent to T2C who complete the TM intervention. (M)aintenance: The percentage and characteristics of PCPs who recommend T2C to appropriate patients upon long-term follow-up, as well as T2C utilization by referred adolescents/parents via de-identified data. The baseline and follow up measures administered are mapped onto each component of the RE-AIM framework.

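### Reach is defined for T2C only, so referral and consent cannot be compared between TAU and T2C, and the planned baseline tests are a weak substitute at about 50 adolescents

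*Combined protocol and SAP*

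**What the plan says.** All references are to the combined protocol and SAP.

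- **Allocation.** Statistical Considerations states: "Prior to study start, each CCP study practice will be randomly assigned to switch from Treatment As Usual (TAU) to the intervention". It adds that "all practices start with TAU (i.e., PCP referral to embedded MH care) and are randomized to transition to implement T2C at different times". The same section also has a web-based system naming the next clinic to start. On either reading, a clinic's phase is fixed before the youths recruited in that phase are identified.
- **Entry.** Youth Exclusion Criteria lists "Not referred to mental health care". Among the alternative symptom routes, Youth Inclusion Criteria ends with "OR provider indicates there is a concern that youth has mood or behavioral problem".
- **Reach.** Statistical Considerations defines it as "The percentage and characteristics of screen-positive adolescents referred for MH treatment who are offered, and agree to participate in, T2C".
- **Adoption.** The same paragraph defines it as "The percentage and characteristics of PCPs who refer to T2C upon making a referral for MH care for a screen-positive adolescent".
- **Comparison and safeguard.** Hypothesis 1b (Study Objectives) compares readiness for care between T2C youths and youths referred under TAU. Study Objectives and Statistical Considerations plan t and chi-square tests of baseline demographic and clinical variables. Variables found to differ enter the mixed models as covariates. The baseline phone call collects readiness, barriers, help-seeking attitudes and treatment history, among other measures.
- **Size.** Aim 1b gives "n=2 clinics, 50 adolescents". The split between TAU and T2C is not stated.

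**The concern.** Randomising the order in which two clinics switch does not balance the individual youths recruited before and after the switch. The PCP is the gatekeeper, and the definition of Adoption implies that in a T2C period the PCP knows the programme is available. Families receive the consent wording before the consent call, so they can know too. Either could change who enters: a PCP may refer a youth who would otherwise not have been referred, or a family may agree because a text programme is on offer.

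If the added youths are more or less open to care, the readiness difference partly reflects who enrolled rather than what T2C did. The direct way to see this is to compare referral and consent rates between phases. Reach and Adoption exist for T2C only, so the visible plan supplies one side of that comparison. Reach is also confined to screen-positive youths, so it does not clearly cover those who enter on provider concern.

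**Working it through.** The documents give no alpha, power, effect size or sample-size derivation, so there is no figure of the plan's own to reproduce. Two checks follow.

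**Inputs.** From the documents: 2 clinics, 50 adolescents, baseline tests followed by adjustment. Assumed: two-sided 0.05, SD 1, independent observations (clustering and calendar time ignored), and a 25:25 split. A 15:35 split is also shown, and 50:50 in case 50 means per clinic.

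**1. How large a gap could selection produce?**

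Spurious difference in means = share of additional youths × their difference in readiness.

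- 20% share, 0.5 SD: 0.2 × 0.5 = 0.10 SD
- 30% share, 0.5 SD: 0.3 × 0.5 = 0.15 SD

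Both inputs are assumptions. The result is before any baseline adjustment, and the direction is unknown.

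**2. Would the planned baseline tests catch a shift?**

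Standard error of a difference in means = sqrt(1/n1 + 1/n2). At 25:25 this is sqrt(2/25) = 0.28 SD. The shift detectable with 80% power = (1.960 + 0.842) × standard error; at 25:25, 2.802 × 0.2828 = 0.79 SD. Power uses the normal approximation.

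| Split | Power, 0.3 SD | Power, 0.5 SD | Shift detectable at 80% |
|---|---|---|---|
| 25:25 | 0.18 | 0.42 | 0.79 SD |
| 15:35 | 0.16 | 0.37 | 0.865 SD |
| 50:50 | 0.32 | 0.71 | 0.56 SD |

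- An exact t calculation at 25:25 gives 0.18 and 0.41. A 0.5 SD shift is therefore missed, and left unadjusted, about 59% of the time (1 − 0.41).
- Detecting 0.5 SD with 80% power needs 63 per group.
- For a binary trait of 30% v 50% at 25:25, power is 0.30.
- For the gaps in step 1, 0.10/0.2828 = 0.35 and 0.15/0.2828 = 0.53 standard errors, which gives power of roughly 6% to 8%.
- With 10 independent baseline tests, the chance of at least one false flag is 1 − 0.95^10 = 0.40.

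**Bias left by testing before adjusting.** A simulation of 6,000 runs (25:25, no T2C effect, baseline-outcome correlation 0.5 assumed) gave the following.

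| True baseline shift | No adjustment (shift × 0.5) | Planned test-then-adjust | Always adjust |
|---|---|---|---|
| 0.3 SD | 0.15 SD | 0.09 SD | 0.00 SD |
| 0.5 SD | 0.25 SD | 0.09 SD | 0.00 SD |

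The planned rule removes part of the bias from a measured trait. No version of it acts on an unmeasured trait, and none shows how many youths were referred or declined under TAU.

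**The case against.** A reader might infer that the trial cannot see or correct any change in who is enrolled. The documents do not support that. Baseline T2C v TAU tests with covariate adjustment are planned, and the battery includes readiness, barriers and attitudes, which lie close to the trait most likely to drive selection. Large measured shifts would be seen and adjusted for. What remains is that moderate shifts would often be missed and unmeasured ones are not addressed.

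Other points on that side:

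- **Reach was written to describe uptake.** Its definition is not faulty for that purpose, and no T2C is offered in TAU. This stands. The gap is that nothing else in the visible text supplies the TAU side.
- **TAU counts may be kept anyway.** The Consent section points to a recruitment methods section that is not in the public text, and the Screening Wizard questionnaire captures the PHQ and the referral without being limited to T2C periods. So one can say only that no phase-by-phase recruitment comparison is specified in the visible text, not that the data will not exist.
- **PCP knowledge is inferred.** It follows from Adoption and from the absence of any described concealment, but is not stated. The written entry criteria are the same in both phases.
- **The provider-concern route may be narrow.** Staff complete the PHQ when it is missing in one of the other routes, and the parent criteria ask for a youth who scores positive. How many would enter on concern alone is unclear.
- **The illustrated bias is small against the noise.** A gap of 0.10 to 0.15 SD is about one third to one half of the 0.28 SD standard error, and in the simulation the false-positive rate under the planned rule stayed near nominal (0.050 and 0.056). This is a feasibility phase. That limits the weight of the point, but recruitment flow by phase is itself feasibility information.

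**Conclusion.** The point holds in a limited form. Clinics are allocated before youths are identified, entry runs through a PCP referral with no concealment described, and Reach covers T2C only. The visible plan therefore cannot compare referral or consent between TAU and T2C. Its existing safeguard reaches only measured differences that turn out significant. At an assumed 25:25 split that means power of about 0.4 for a 0.5 SD shift (0.37 at 15:35, 0.71 at 50:50).

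The size of any actual bias is unknown. The 0.10 to 0.15 SD figure rests on assumed shares and an assumed 0.5 SD difference, before baseline adjustment, and is not an estimate for this trial. This is a cheap improvement, not a flaw that invalidates the comparison. It is worth making early because TAU counts may be hard to recover later.

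**What to change.** Apply the Reach measure to both phases. By clinic and phase, record the numbers PHQ-positive, referred, approached and consented, with age, sex and PHQ score, and report referral and consent rates for TAU v T2C.

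Add a sensitivity analysis of readiness limited to PHQ-positive youths in both phases. State that it is a partial check: it removes the provider-concern route but still conditions on referral and consent. The counts mainly reveal selection and do not remove it. Prespecified adjustment for baseline readiness, which is already collected, would complement them for the measured part.

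Cost: slightly more screening data handling, one further analysis, and a smaller sample in that analysis. The documents define the Reach metric but describe no log behind it, so the collection in both phases should be written down.
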